Appendix 8 Sample size determination

Part 1: Estimated efficacy (Day 28 PCR-corrected ACPR) of FQ 200, 400, 600 and 900 mg administrated in presence of OZ439 TPGS for different levels of baseline parasitemia

Clinical trial simulations were used, consisting of simulating FQ concentrations at Day 7, baseline parasitemia, and then PCR-corrected ACPR at Day 28 using a model linking ACPR at Day 28 probability to FQ concentration at Day 7 and baseline parasitemia.

The model (eq 1) was a logistic regression modeling PCR corrected ACPR at Day 28 probability (p) as a function of FQ concentration at Day 7 (ConcD7FQ), Artesunate (AR) indicator (no/yes) and baseline log10-parasitemia. It was developed from DRI10382 data: African patients, Per Protocol population, excluding patients with reinfections, using the 4 arms of the DRI10382 (FQ 4 mg/kg or AR + FQ 2, 4 or 6 mg/kg, repeated doses). Two types of analyses were done, classifying as failure or excluding patients with rescue therapy before/without failure, and finally the results of the analysis excluding patients were favored, to compensate for the possible underestimation of FQ single dose effect (model built on repeated doses). In this analysis based on 223 patients, the FQ efficacy was estimated to be ACPR28corr=80.9% (95% Confidence Interval [CI]: 66.7% to 90.9%) in arm FQ 600 mg.

(eq 1)
$$log(p/(1-p)) = \alpha + \beta FQ.ConcD7FQ + \beta AR. (AR=yes) + \beta BasePar.log10(BasePar)$$

FQ concentrations at Day 7 (168 h post dose) were simulated from the FQ PopPK model updated from DRI12805 (POH0456) for TPGS formulation and single dose administration, in an African adult population (weights resampled from 194 profiles of African adults of DRI10382 and DRI12805 cohort 1A and 1B, of median weight 55 kg and median age 21 years). Log-normal distributions were fitted to these simulated concentrations and then used for simulation.

Baseline parasitemia was simulated for different scenarii, using truncated log-normal distributions. The base assumption was a baseline parasitemia greater than 1000 parasites/ μ L and of median about 10,000 parasites/ μ L. Some other scenarii were considered: baseline parasitemia greater than 3000, 5000, or 10,000 parasites/ μ L, with a maximum fixed at 5.5 log10 parasites/ μ L. In the following, the baseline parasitemia greater than 3000 parasites/ μ L scenario was selected to ensure a better enrollment of patients during the study.

Based on N=10,000 simulations/arm and S=1000 simulations for the model parameters uncertainty, the results showed a PCR-corrected ACPR at Day 28 estimated at 72% (90%CI: [57% to 84%]) for FQ 400mg alone and 79% (90%CI: 67% to 87%) for FQ 600 mg alone for a baseline parasitemia greater than 3000 parasites/ μ L. Finally the FQ fixed dose of 400 mg was selected.

Part 2: Estimated power for various sample size of an OZ439 exposure-effect analysis, considering the fixed FQ dose, the 4 selected OZ439 dose levels (0, 300, 600, 1000 mg) and the selected baseline parasitemia

Simulation of clinical trials

Clinical trial simulations were used to simulate trials of 4 arms with a fixed dose of 400 mg FQ and 4 dose levels of OZ439 (0, 300, 600, and 1000 mg) for a baseline parasitemia greater than 3000 parasites/µL. FQ and OZ439 concentrations at Day 7 (168 h post dose) were simulated using log-normal distributions that were adjusted to concentrations obtained from the FQ PopPK model and from the OZ439 PopPK model in an African adult population (as in part 1), and were assumed to be slightly correlated. Truncated log-normal distributions were used to simulate baseline parasitemia greater than 3000 parasites/µL in log10Par/µL by a normal distribution: mean=4, SD=0.55, minimum=3.48; maximum=5.5 (minimum and maximum for the truncation). Day 28 PCR-corrected ACPR was simulated using a "hypothetical" model linking ACPR at Day 28 probability to FQ and OZ439 concentration at Day 7 and baseline parasitemia.

The "hypothetical" logistic regression model (eq 2, see below) used for simulations was a composite of the "PQP/OZ-ACPR28 model" built by MMV, modeling PCR-corrected ACPR at Day 28 probability (p) as a function of OZ439 and PQP concentrations at Day 7 and baseline log10-parasitemia, and of assumptions made on FQ efficacy, which were based on the results of part 1. Precisely, β FQ was fixed at 0.12 by calibration to get ~ 72% success ACPR at Day 28 for FQ 400 mg alone for a baseline parasitemia greater than 3000 parasites/ μ L, and the following parameters were extracted from the MMV model: α =3.23, β OZ439 = 0.73, and β BasePar = -1.27.

(eq 2)
$$log(p/(1-p)) = \alpha + \beta FQ.ConcD7FQ + \beta OZ439.ConcD7OZ + \beta BasePar.log10(BasePar)$$

Using all these assumptions, the PCR-corrected ACPR at Day 28 rates simulated in the 4 arms FQ 400 mg \pm OZ439 at 0, 300, 600 and 1000 mg were of 72%, 81%, 91%, and 97% for a baseline parasitemia greater than 3000 parasites/ μ L.

Clinical trials analyses

Exposure-effect analyses of the simulated clinical trials were performed, consisting of a logistic regression model of exposure at Day 7 for both drugs, with baseline parasitemia as covariate, and the Day 28 PCR-corrected ACPR as response variable (as in eq 2 above). Significance of OZ439 concentration effect (βOZ439) was analyzed using a 2-sided alpha Wald test at 5%.

Overall, five thousand trial simulations were performed, and the power was deduced as the percentage of significant simulated trials. Results estimated that 30 evaluable participants per treatment arm will yield a power around 90% to detect an OZ439 concentration effect relation (in a population of patients with a baseline parasitemia greater than 3000 parasites/ μ L, for 4 arms FQ 400 mg + OZ439 at 0, 300, 600, and 1000 mg).

Around 15 % of early dropout is anticipated, consequently approximately 35 participants are to be included in each arm (to get 30 evaluable participants/arm) resulting in approximately 140 participants to be enrolled in the whole study.

Property of the Sanofi group - strictly confidential

Clinical Trial Protocol ACT14655 – artefenomel/ferroquine 13-Nov-2017 Version number: 1

A rather large uncertainty was attached to the models and to the different assumptions used to perform the simulations, so these results are approximate.

13-Nov-2017 Version number: 1

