5.4 SCIENTIFIC RATIONALE FOR STUDY DESIGN

There are 3 aspects to consider to define most appropriate baseline parasitemia for the selection of the participants in the study:

- Baseline parasitemia is a strong covariate of parasiticidal activity and clinical efficacy. A
 phase 2b study testing OZ439 and PQP performed by MMV (MMV_OZ439_13_003)
 showed that baseline parasitemia is strongly correlated with clinical efficacy (Day 28
 PCR-corrected ACPR), meaning that efficacy may increase when baseline parasitemia
 decreases, making more difficult to show a significant difference in efficacy across study
 arms. On the other hand increasing baseline parasitemia may not facilitate the recruitment
 of adult participants living in endemic places.
- There is also a need to minimize the risk of re-infection during the trial in participants receiving FQ 400 mg to keep sufficient evaluable patients in each arm while allowing to enroll 140 patients in a reasonable timeframe and discriminating levels of activity across study groups. A baseline parasitemia of ≥3000 parasites/µl is a good compromise that would meet both requisites and allow participants recruitment in places with moderate transmission and low risk of re-infection during the study.
- A baseline parasitemia ≥3000 parasites/µl is deemed to enlarge candidate site list, accelerate participant recruitment and minimize risk of re-infection during the study while keeping an adequate power. It will also minimize the risk of progression to severe malaria in a context of low dose of OZ439 in some groups.

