5.5 JUSTIFICATION FOR DOSE

Malaria therapy is constrained by WHO's guidance that is recommending to treat an uncomplicated *P. falciparum* malaria with a combination of 2 highly potent and active drugs having a different mode of action with the objective to treat the infection and prevent resistance to the drugs (6).

The efficient minimal dose of FQ will be confirmed in the ongoing phase 2b trial (DRI12805). However, there is some evidence that FQ is a highly potent drug. Therefore it may be difficult to show a significant effect ranging of OZ439 within the combination if the FQ dose level is too high.

In this study, a dose of 400 mg of FQ was selected (this is one of the doses tested in the DRI12805). This dose is low enough to leave room for added efficacy attributed to OZ439. This dose will minimize the risk to see FQ effect hiding OZ439 effect and optimize the chance to show an effect ranging across the 4 groups tested in this study. Modeling and simulations indicate that efficacy of FQ 400 mg when given alone (PCR corrected Day 28 ACPR) may be around 72%, leaving room for increased efficacy related to OZ439 to less than 20%.

Participants enrolled in some of the 4 groups of the study might receive sub-therapeutic dose of drug combination, however only adults and adolescents as of 14 years of age and presenting with uncomplicated malaria with $\leq 50,000$ asexual parasites/ μ L of blood will be enrolled, both measures mitigating the risk of development of a severe malaria. They will be hospitalized for at

Property of the Sanofi group - strictly confidential

least 48 h in a well-equipped health center and will receive a standard rescue therapy as soon as there is evidence of treatment failure. In addition to initial hospitalization, patients will have frequent assessments (biweekly after the hospitalization through Day14 and weekly thereafter through the end of the study), and they will receive a rescue therapy at Day 28 even without signs of treatment failure. All these measures will mitigate the risk of malaria management failure.

To optimize the likelihood to observe a difference on the primary endpoint (Day 28 PCR corrected ACPR) over the various doses of OZ439, FQ 400 mg will be administered alone or with OZ439 at a dose of 300, 600 or 1000 mg, while OZ439 800 mg is being tested in the ongoing OZ439/FQ DRI12805 phase 2b study.

The rationale to include a group receiving 1000 mg of OZ439 is based on:

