6.1 INCLUSION CRITERIA

Participants are eligible to be included in the study only if all of the following criteria apply:

Age

I 01. Participant must be 14 to 69 years of age inclusive, at the time of signing the informed consent.

Type of participant and disease characteristics

I 02. Participants who present with uncomplicated *P. falciparum* malaria, with a fever as defined with axillary temperature ≥37.5 degree Celsius (°C) or oral/ rectal/ tympanic temperature ≥38°C or history of fever in the previous 24 hours (history of fever must be documented), with a mono-infection with *P. falciparum* and parasitemia (microscopically, blood smear) ≥3,000 and ≤50,000 asexual parasites/µL of blood.

Weight

I 03. Body weight within 35 and 90 kg (inclusive).

Sex

- I 04. Male and female
 - a) Male participants: A male participant must agree to use contraception as detailed in Appendix 5 of this protocol for 3 months after the last dose of study treatment and refrain from donating sperm during this period.
 - b) Female participants: A female participant is eligible to participate if she is not pregnant (see Appendix 5), not breastfeeding, and at least one of the following conditions applies:
 - Not a woman of childbearing potential (WOCBP) as defined in Appendix 5

OR

- A WOCBP who agrees to follow the contraceptive guidance in Appendix 5 for 3 months after the last dose of study treatment.

Informed Consent

I 05. Capable of giving signed informed consent (if the patient is ≥age defining majority) as described in Appendix 3, which includes compliance with the requirements and restrictions listed in the informed consent form (ICF) and in this protocol. Informed consent signed by the legally acceptable representative (LAR) of the minor patient (<18 years of age or <other age locally defining majority). In addition, in accordance with local regulation, minor participants with capacity for writing could sign off on an Assent Form. For those who are able to understand but with no capacity for writing the Assent Form would be read. In that case, an impartial witness could certify the document was read to the child.

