10 STATISTICAL CONSIDERATIONS

10.1 SAMPLE SIZE DETERMINATION

The strategy for selecting fixed FQ dose, baseline parasitemia, and sample size was composed of two parts:

- 1. Estimated efficacy (Day 28 PCR corrected ACPR) of FQ 200, 400, 600 and 900 mg administrated in presence of OZ439 TPGS for different levels of baseline parasitemia
- 2. Estimated power for various sample size of an OZ439 exposure-effect analysis, considering the fixed FQ dose, the 4 selected OZ439 dose levels (0, 300, 600, 1000 mg) and the selected baseline parasitemia

Details of the method are provided in Appendix 8.

Results estimated that 30 evaluable participants per treatment arm will yield a power around 90% to detect an OZ439 concentration effect relation (in a population of patient with a baseline parasitemia greater than 3000 parasites/ μ L, for 4 arms FQ 400 mg + OZ439 at 0, 300, 600, and 1000 mg).

Around 15 % of early dropout is anticipated, consequently approximately 35 participants are to be included in each arm (to get 30 evaluable participants/arm) resulting in approximately 140 participants to be enrolled in the whole study.

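### The power of around 90% was simulated with baseline parasitemia up to about 316,000/µL, but I02 admits at most 50,000/µL, so 12% of the simulated patients are ineligible

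*Protocol*

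**What the plan says.** Protocol 10.1 states that "30 evaluable participants per treatment arm will yield a power around 90% to detect an OZ439 concentration effect relation". Appendix 8 gives the method and SAP 1.3 repeats it.

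- **Part 2 (power).** Log10 baseline parasitemia is normal with "mean=4, SD=0.55, minimum=3.48; maximum=5.5 (minimum and maximum for the truncation".
- **Part 1 (success on ferroquine alone).** The parasitemia scenarios are run "with a maximum fixed at 5.5 log10 parasites"/µL. For the scenario above 3,000/µL they give 72% Day 28 PCR-corrected ACPR for FQ 400 mg alone, with a 90% CI of 57% to 84%.
- **Link between the parts.** In the Part 2 model (eq 2) the ferroquine coefficient "was fixed at 0.12 by calibration to get ~ 72% success ACPR at Day 28 for FQ 400 mg alone". The other coefficients are α = 3.23, βOZ439 = 0.73 and βBasePar = −1.27.
- **Eligibility.** I02 in Protocol 6.1 requires "≥3,000 and ≤50,000 asexual parasites" per µL, and Protocol 5.5 relies on the same upper limit. SAP 2.3.5.1 lists breaches of I02 among the protocol violations for the primary PK/PD efficacy population.
- **Role of parasitemia.** Protocol 5.4 says: "Baseline parasitemia is a strong covariate of parasiticidal activity and clinical efficacy". It adds that efficacy may rise when baseline parasitemia "decreases, making more difficult to show a significant difference in efficacy across study" arms.

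**The concern.** The lower truncation point was matched to I02 (3.48 = log10 3,000). The upper one was not: log10 50,000 is 4.70, not 5.5. The sample-size text describes the population only as above 3,000/µL and never applies the upper limit.

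The simulated trials therefore contain patients whom the real trial excludes, and by the protocol's own reasoning these are the patients most likely to fail. With planned success of 72% to 97%, failures are the scarce outcome and largely determine the power of the Wald test on OZ439 exposure. Removing the high tail should leave power equal or lower. At stake is whether the figure that justifies 30 evaluable patients per arm applies to the patients who will be enrolled.

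**Working it through.** **1. Ineligible share (exact).** Inputs from Appendix 8: mean 4, SD 0.55, limits 3.48 and 5.5. Input from I02: log10 50,000 = 4.699.

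P(>50,000) = [Φ((5.5−4)/0.55) − Φ((4.699−4)/0.55)] / [Φ((5.5−4)/0.55) − Φ((3.48−4)/0.55)] = [Φ(2.727) − Φ(1.271)] / [Φ(2.727) − Φ(−0.945)] = 0.1197, that is 12.0%.

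By the same formula 3.8% exceed 100,000/µL. Mean log10 parasitemia is 4.164 as simulated and 4.059 with the cap; the medians are about 13,100 and 11,200/µL.

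**2. Direction.** With βBasePar = −1.27, the shift in the mean raises the logit by about 1.27 × (4.164 − 4.059) = 0.13. The planned rates of 72/81/91/97% give 30 × (0.28 + 0.19 + 0.09 + 0.03) = 17.7 expected failures among 120 patients. Under the cap with eq 2 unchanged, one setting (FQ CV 30%, OZ439 CV 30%) gives 74.6/83.1/92.2/97.5%, hence 30 × (0.254 + 0.169 + 0.078 + 0.025) = 15.8.

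**3. Power.** The documents give no medians or spreads for the Day 7 concentrations and describe their correlation only as slight. I assumed log-normal concentrations with FQ CV 0.3 to 0.7, OZ439 CV 0.4 to 1.0 and correlation 0 or 0.3, which makes 18 scenarios. Medians were solved so that eq 2 with maximum 5.5 gives 72/81/91/97%. Each trial had 30 patients per arm and was fitted by logistic regression on FQ, OZ439 and log10 parasitemia, with a two-sided 5% Wald test on OZ439. There were 3,000 trials per cell; the Monte Carlo SE of a difference is about 0.9 point.

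With maximum 5.5, power was 88.7% to 94.6%, so the stated figure is reproduced. The eight scenarios that start between 88% and 92% are shown below (power in %).

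| FQ CV, OZ439 CV, correlation | Max 5.5 | Cap, eq 2 unchanged | Cap, FQ alone 73% | Cap, FQ alone 72% |
|---|---|---|---|---|
| 0.3, 0.4, 0 | 91.2 | 86.7 | 89.9 | 91.5 |
| 0.3, 0.4, 0.3 | 90.7 | 86.4 | 89.6 | 91.5 |
| 0.3, 0.7, 0 | 91.4 | 84.7 | 89.1 | 90.8 |
| 0.3, 0.7, 0.3 | 90.8 | 84.4 | 89.0 | 91.1 |
| 0.3, 1.0, 0 | 89.5 | 81.4 | 86.2 | 89.1 |
| 0.3, 1.0, 0.3 | 88.7 | 80.4 | 85.7 | 88.6 |
| 0.5, 1.0, 0 | 91.2 | 84.9 | 89.0 | 90.6 |
| 0.5, 1.0, 0.3 | 91.0 | 84.1 | 88.8 | 90.9 |

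In these eight the loss is 4.3 to 8.3 points with eq 2 unchanged, 1.1 to 3.3 points at 73%, and nil within simulation error at 72%. Over all 18 scenarios the ranges are 2.3 to 8.3 points (median 5), 0.7 to 3.3 points, and −0.8 to +0.6 points.

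A separate simulation with 5,000 trials per setting gave 89–92% falling to 82–87% with eq 2 unchanged, and a loss of 0 to 1 point with FQ alone reset to 72%. Runs with other seeds or scenarios reached about 9 points with eq 2 unchanged. At OZ439 CV 150% the loss was 7.5 to 11 points, but power with maximum 5.5 was then only 83–87%, so those settings do not match the plan.

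**4. Which column applies?** The 72% itself comes from Part 1 with maximum 5.5. Its value under the cap depends on the parasitemia slope in eq 1, which is not given. If that slope is 0 the rate stays at 72.0%. It becomes 72.8–73.1% at −0.5, 73.6–74.2% at −1.0, and 74.0–74.8% at the −1.27 of eq 2 (assuming FQ CV 30–70% and an FQ term of 1.5 to 3 on the logit at the median). A slope of zero sits badly with Protocol 5.4.

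**The case against.** The strongest reply is that nothing is miscalculated. The stated power reproduces, the text describes the population as above 3,000/µL, and Appendix 8 itself warns that large uncertainty attaches to the models and assumptions and that the results are approximate. That uncertainty is much larger than this effect. In three scenarios with maximum 5.5, moving success on ferroquine alone across its stated 90% CI of 57% to 84% moved power from about 99.8% down to 29–38%, whereas the cap moves that success rate by 0 to 3 points. The upper end of the loss also requires the ferroquine coefficient to stay frozen; repeating the calibration to 72% under the cap removes the loss. Finally, the simulation uses Day 7 concentration, while the planned primary model uses AUC and chooses covariates by fit statistics.

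Most of this stands as a limit on weight. The error is one of input, not of calculation, and its consequence could be nil. The claim that power can only be equal or lower assumes that the mean of 4 and SD of 0.55 still describe patients within 3,000–50,000/µL. It does not dispose of the point, however. A general caveat does not disclose that one input contradicts I02. The wide interval is uncertainty around an estimate, whereas this is an avoidable mismatch. And to apply 72% to the eligible range is an assumption that the plan does not state, because that figure was derived with the same 5.5 maximum.

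**Conclusion.** The concern holds. The mismatch and the 12.0% are exact and need no assumption. The effect on power is conditional: about 0 to 9 points lower for the eligible range, according to how the 72% is recalibrated and to the assumed concentration spreads and correlation. Keeping the stated model gives the larger losses; taking 72% to hold within 3,000–50,000/µL gives none.

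The importance is minor to moderate. Of the simulated patients 88% are within I02, and power stays at about 80% or more in the settings that reproduce the plan's figure. The trial is not shown to be too small. What is shown is that around 90% was computed for a population that the trial partly excludes.

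**What to change.** Rerun the Part 1 calibration and the Part 2 power simulation with the maximum set to log10(50,000) = 4.70, using the sponsor's own concentration distributions, correlation and eq 1 coefficients. State the resulting power, and the parasitemia range it refers to, in Protocol 10.1, Appendix 8 and SAP 1.3. If 72% on ferroquine alone is retained for 3,000–50,000/µL, say so and give the reason.

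The cost is one changed limit, a rerun of existing code and text edits in three places. No patients or visits are added, and neither the design nor the primary test changes. The stated power may come out less favourable.

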IRT:	Interactive Response Technology
ITT:	intent-to-treat
IVRS:	Interactive Voice Response System
LCF:	Late Clinical Failure
LLT:	Lower Level Term
LOQ:	Limit of Quantification
LPF:	Late Parasitological Failure
MedDRA:	Medical Dictionary for Regulatory Activities
mITT:	modified-intent-to-treat
PCR:	Polymerase Chain Reaction
PCSA:	Potentially Clinically Significant Abnormality
PCT:	parasite clearance time
PP:	per-protocol
PR:	Parasite Reduction
PRR:	Parasite Reduction Ratio

PT:	Preferred Term
qPCR:	quantitative polymerase chain reaction
RT-qPCR:	quantitative reverse transcription polymerase chain reaction
SAEs:	Serious Adverse Events
SMQ:	standardized MedDRA query
SOC:	System Organ Class
TBILI:	Total bilirubin
TEAE:	Treatment emergent Adverse Event
TPC50:	Time until reduction by 50% of parasitemia
TPC99:	Time until reduction by 99% of parasitemia
TPGS:	alpha tocopherol polyethylene glycol 1000 succinate
WHO-DD:	World Health Organization-Drug dictionary

1 OVERVIEW AND INVESTIGATIONAL PLAN

1.1 STUDY DESIGN AND RANDOMIZATION

A phase 2a, randomized, open label, parallel-group study, single-dose regimen, testing 3 dose levels of OZ439 given in combination with FQ and FQ alone in participants with uncomplicated *P. falciparum* malaria.

After a screening phase of up to 1 day before the single dose administration, patients are randomized (stratified by investigative site) via Interactive Response Technology (IRT) in a 1:1:1:1 ratio to 1 of the 4 treatment groups.

Balance across a group of blocks will be achieved by considering a Latin square design feature during the generation of the randomization schedule. This approach is being used to provide better balance of study level treatment assignments as compared to conventional random of sampling for blocks.

[figure not shown]
12 blocks size (of size 8) will be attributed to each site and will be balanced across the group block entries, as well as within each block. The full randomization list will be comprised of the records which make up twelve 8 x 8 Latin squares ($12 \times 8 \times 8 = 768$ records in total). The sequence of treatment groups within each block will be random.

Approximately 140 patients (35 patients per treatment group) will be recruited and randomized in order to have 120 evaluable patients (30 patients per treatment group) from approximately 8 to 10 sites.

Adults up to 69 years old and adolescents as of 14 years old will be included in 4 parallel arms in a 1:1:1:1 randomization ratio. Randomization will occur the day of or up to 1 day after screening procedures.

Participants will receive one of the 4 treatments: FQ 400 mg alone or combined with OZ439 300 mg, 600 mg, or 1000 mg.

The graphical presentation of the study design on the single-dose treatment is provided in Figure 1.

Note: Visits 1 & 2 can occur on the same day ; Visit 13 : assessment of primary endpoint

